### **6.3.2. List of Data Source Materials and Measures (Table 2 below).**

**Student Survey:** To assess students' participation in N/E, we draw from several existing measurements that have been implemented and validated in research studies with AI youth. Primary outcome measure: Condom use will measure frequency of condom use relative to frequency of sex during sexual intercourse using questions derived from the Risk Behavior Assessment. Secondary outcome measures: These will include the number of sex partners; age of onset of sexual intercourse; frequency of sexual intercourse; pregnancy history; frequency and type of birth control used during sexual intercourse relative to the frequency of sexual intercourse; and frequency and types of substance use (cigarettes, marijuana, alcohol, and methamphetamine). Tertiary outcome measures: Parent/legal guardian communication is measured by the frequency and types of SRH topics that parent/legal guardian and child discussed. Cultural identity is measured using two established measurements: One measure assesses the extent to which a student identifies with his or her American Indian culture and feels cultural pride, and the other measure assesses frequency and type of participation in cultural activities. Access to SRH services is measured by frequency and type of SRH service used (ever been tested for STIs and follow-up, ever been tested for HIV and follow-up, ever been tested for HCV and follow-up, ever been pregnant/gotten someone pregnant and follow-up). Other variables to be measured in N/E that assess attitudes, intentions, skills, and mental health are: Motivation to avoid STIs, HIV, HCV, and pregnancy, as measured by asking students how important it is to them to keep themselves (or someone else) from getting an STI, HIV, and HCV, and how important it is to them to keep from getting pregnant or getting someone pregnant. Intention to use condoms and/or birth control is measured by asking students how likely it is they will use condoms and/or birth control the next time they have sexual intercourse. Intention to abstain from sex is measured by asking students how likely it is that they will not participate in sexual intercourse. Condom and birth control use self-efficacy is measured by assessing confidence in one's ability to use condoms and birth control. Refusal skills regarding sex are assessed by how strongly students believe they can say no to sex. Knowledge about STIs, HIV, HCV, pregnancy, and healthy relationship characteristics are measured using true/false/don't know questions. Mental health is assessed using two established measures: One measure assesses depression using the C-ESD, and the other measurement assesses exposures to stressful life events by assessing lifetime occurrences of a series of negative events. Standard demographic measures in the student survey are age, gender, sexual orientation, school, and highest grade completed.

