**Table 2. NIE Measures.**

**Table 2. N/E Measures.**

Data Collection Instruments and Measures	Data Collection: Baseline & Months				Description of Measures Number of Items; Scale Anchors; Benchmark Values	
	Base	3	9	12		
Student Survey						
Primary Outcome Variable						
Proportion of condom use during sexual intercourse (SI)	X	X	X	X	2 items; number of times condom used relative to number of times had SI	
Secondary Outcome Variables						
Age of onset of sexual intercourse	X	X	X	X	2 items; ever had SI & age at first SI	
Number of sex partners	X	X	X	X	2 items; lifetime & past-month sex partners	
Frequency of sexual intercourse	X	X	X	X	1 item; frequency of SI in past month	
Pregnancy history	X	X	X	X	1 item; number of pregnancies	
Type & frequency of birth control (BC) during sexual intercourse	X	X	X	X	3 items; type of BC use and number of times BC used during SI	
Type & frequency of substance use (SU) during sexual intercourse	X	X	X	X	1 item measures SU with SI; 5 items measure lifetime and past month SU	
Tertiary Outcome Variables						
Type & frequency of parent/legal guardian-child SRH communication	X	X	X	X	24 items Likert scale; higher score = higher communication	
Cultural identity & participation in cultural activities	X	X	X	X	3 items cultural identity ( $\alpha = .75$ ); 2 items cultural activities engagement ( $\alpha = .46$ )	
Type & frequency of SRH services	X	X	X	X	9 items; frequency, type, and follow-up of SRH services used	
Other Variables						
Motivation to avoid STIs, HIV, HCV, & pregnancy	X	X	X	X	Up to 9 items; 1 (very true) to 5 (very untrue); 1 = more positive attitude/motivation	
Condom & birth control use intention & self-efficacy	X	X	X	X	4 items per intention; 1 (very true) to 5 (very untrue); 1 = higher intention; 6 self-efficacy items; 1 (very easy) to 4 (very hard); 1 = high self-efficacy	
Abstinence	X	X	X	X	3 items; 1 (strongly disagree) to 4 (strongly agree); 4 = more supportive of teen abstinence	
Refusal skills regarding sex	X	X	X	X	7 items; 1 (I definitely can say no) to 5 (I definitely can't); 1 = stronger refusal skills	
Knowledge of STIs, HIV, HCV, pregnancy, & health relationships	X	X	X	X	Range of 4 to 10 items per topic; True/False/DK; Average proportion of questions correct	
Depression (CES-D) & exposure to stressful life events	X	X	X	X	CES-D — 7 items ( $\alpha = .80$ ); Life Events — 24 items; Yes/No; number of events observed	
Student Demographics						

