H1: AI youth who participate in N/E will demonstrate increased condom use at 3, 9, and 12 months. (12 months will be used in the Primary Outcome analysis; 3 and 9 months will be used in the Secondary Outcomes analysis.) H2: AI youth who participate in N/E will demonstrate increased use of other birth control at 3, 9, and 12 months. They also will demonstrate a decrease in sexual risk behaviors as measured by reduced number of sex partners, delayed onset of sexual intercourse, and decreased substance use during sex, at 3, 9, and 12 months. (Secondary Outcomes) H3: N/E parents/legal guardians and youth will demonstrate significantly increased communication about topics related to SRH at 3, 9, and 12 months. AI youth who participate in the cultural mentoring program will demonstrate significantly increased understanding of cultural values related to traditional AI beliefs regarding SRH at 3, 9, and 12 months. And AI youth who participate in N/E will report significantly increased use of SRH services at 3, 9, and 12 months as a result of improved coordination among education, health care, and social service agencies on the Fort Peck Reservation. (Tertiary Outcomes) AIM 3: Evaluate the fidelity and acceptability of N/E. N/E's fidelity and acceptability will be evaluated using qualitative methods, including focus groups, activity logs, and staff field notes and meetings.

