### Secondary Outcome Measure:

2. Change in delayed onset of sexual intercourse at 3 months, 9 months and 12 months

Changes in delayed onset of sexual intercourse will be measured intercourse with 2 items (ever had sexual intercourse and age at first sexual intercourse)

[Time Frame: 3 months, 9 months and 12 months]

3. Change in decreased number of sex partners at 3 months, 9 months and 12 months  
Change in decreased number of sex partners will be measured by 2 items ( lifetime of sex partners and the number of sex partners in the past month)  
[Time Frame: 3 months, 9 months and 12 months]
4. Change in frequency of sexual intercourse at 3 months, 9 months and 12 months  
Change in frequency of sexual intercourse will be measured with 1 time ( frequency of sexual intercourse in the past month)  
[Time Frame: 3 months, 9 months and 12 months]
5. Change in number of pregnancies at 3 months, 9 months and 12 months  
Change in number of pregnancies will be measured with 1 item (number of pregnancies)  
[Time Frame: 3 months, 9 months and 12 months]
6. Change in increased use of birth control during sexual intercourse at 3 months, 9 months and 12 months  
Change in the increased use of birth control during sexual intercourse will be measured with 3 items (type of birth control used and number of times birth control was used during sexual intercourse)  
[Time Frame: 3 months, 9 months and 12 months]
7. Change in decreased alcohol/drug use concurrently sexual intercourse at 3 months, 9 months and 12 months  
Change in decreased alcohol/drugs used concurrently with sexual intercourse will be measured with 1 item ( substance use with sexual intercourse)  
[Time Frame: 3 months, 9 months and 12 months]

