5.11 How many times have you been pregnant or gotten someone pregnant?

- a. 0 times
- b. 1 time
- c. 2 or more times
- d. Not sure

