5.12 Have you ever been tested for HIV, the virus that causes AIDS?

- a. Yes
- b. No
- c. Not sure

5.13 Have you ever been tested for other sexually transmitted diseases (STDs), such as genital herpes, chlamydia, syphilis, or genital warts?

- a. Yes
- b. No
- c. Not sure

5.14 Have you ever been told by a doctor or nurse that you had the HIV infection or any other sexually transmitted disease (STD)?

- a. Yes
- b. No
- c. Not sure

If yes, did you receive follow-up care? Yes No Not sure

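### The service-use outcome in Section 6.3.2 includes pregnancy itself, so a pregnancy moves H3 in the programme's favour while counting against it as a secondary outcome

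*Combined protocol and SAP*

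**What the plan says.** Section 6.3.2 (Student Survey, tertiary outcomes) states that "Access to SRH services is measured by frequency and type of SRH service used". The list that follows names testing with follow-up for STIs, HIV and HCV, for example "ever been tested for STIs and follow-up", and ends with "ever been pregnant/gotten someone pregnant and follow-up". Table 2 describes the measure as "9 items; frequency, type, and follow-up of SRH services used". It does not say which survey questions are the nine, or how they are combined.

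H3, in the registry record included with the protocol, predicts that "AI youth who participate in N/E will report significantly increased use of SRH services at 3, 9, and 12 months" and attributes the rise to better coordination between agencies. Section 3.1.5 (Generalized linear mixed-effects models) treats the H3 outcomes as continuous responses.

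Pregnancy is also a secondary outcome, both in Table 2 and in the registry: "Change in number of pregnancies at 3 months, 9 months and 12 months".

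In the student survey, item 5.11 asks "How many times have you been pregnant or gotten someone pregnant", and no question about care follows it. Item 5.14 asks "Have you ever been told by a doctor or nurse that you had the HIV infection" or another STD, and item 5.16 asks the same about hepatitis C. Each has a follow-up-care question for students who answer yes. Students who have never had intercourse are told at 5.1 to skip the rest of Section 5.

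**The concern.** A test, a clinic visit and follow-up care are services. A pregnancy is an event that the programme aims to prevent. Once it sits inside a service-use measure whose increase is read as success, the measure responds to two things in the same direction: better access, and more pregnancies. A rise produced by pregnancies would be reported as improved coordination of services. If the programme prevents pregnancies, the measure loses part of the rise that better testing would have produced. The H3 result and the pregnancy result could then pull against each other for reasons unrelated to access.

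A weaker form of the problem affects infection. Follow-up care is a service, but the survey lets a student report it only after reporting a diagnosis.

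**Working it through.** The plan gives no figure for this outcome, so there is none to reproduce. The check maps the definition to the printed survey, then sizes the effect under stated assumptions.

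**1. Components in Section 6.3.2 against survey items**

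| Component | Item for the component | Item for follow-up |
|---|---|---|
| HIV testing | 5.12 | after 5.14, only if diagnosed |
| STI testing | 5.13 | after 5.14, only if diagnosed |
| HCV testing | 5.15 | after 5.16, only if diagnosed |
| Pregnancy | 5.11 (lifetime count) | none |

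The three testing rows start from a service. The pregnancy row starts from the event and has no service question behind it, so it can be filled only by the event.

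**2. Direction.** H3 reads an increase as benefit, and the response is modelled as continuous. The natural reading is a score or count in which higher is better. On that reading, 5.11 adds to benefit here and to harm in the secondary tier.

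**3. Which nine items?** The candidates are 4.1 to 4.5 (5), 5.11 (1), three testing items (3), two diagnosis items (2) and two follow-up questions (2): 5 + 1 + 3 + 2 + 2 = 13. At least two subsets give nine:

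- (a) 4.1, 5.11, three tests, two diagnoses, two follow-ups: 1 + 1 + 3 + 2 + 2 = 9.
- (b) 4.1 to 4.5, 5.11, three tests: 5 + 1 + 3 = 9.

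Set (a) fits the mention of follow-up in Table 2 better. Set (b) fits the survey's labelling of all of Section 4 as a tertiary outcome. Both contain 5.11, which Section 6.3.2 requires. The number of items that depend on a pregnancy or diagnosis is five in (a) and one in (b), so the share cannot be fixed from the documents.

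**4. Size (illustration).** Assume an unweighted sum of yes answers, with 5.11 scored 1 for any pregnancy. None of this is in the documents.

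- One student: a service visit and all three tests score 1 + 3 = 4. Adding a pregnancy gives 5. Adding instead an STI diagnosis with follow-up gives 5 if only follow-up is scored, or 6 if the diagnosis is scored too.
- Mean, pregnancy only: if a proportion p of students avert a pregnancy, the mean is lower by p × 1. For p = 0.02 to 0.10 this is 0.02 to 0.10 points. At the upper end it cancels a 10-percentage-point rise in any one testing item.
- Mean, with diagnoses also averted in a proportion d and an assumed 80% follow-up: the shift is p + 0.8d if follow-up is scored, and p + d + 0.8d if the diagnosis is scored as well. With p = d = 0.02 these are 0.036 and 0.056. With p = d = 0.10 they are 0.18 and 0.28.

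Each shift is relative to what the score would have been without the prevention.

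**5. Skip rule.** Students who have never had intercourse do not see 5.11 to 5.16, so their testing answers are absent unless a rule assigns them. Delayed onset is a secondary outcome, so success there removes service-use data from the students concerned.

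**The case against.** The strongest reply is that the plan specifies no score. Table 2 gives a direction for the communication scale but none for services. Pregnancy might be meant only to identify who needs follow-up care, and pregnancy testing and prenatal care are services that the programme addresses. This shows that the size is unknown. It does not rescue the definition: no pregnancy follow-up question is printed, so the component cannot be scored from care received.

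Several stronger readings are tempting, and the objections to them stand:

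- A reader might infer that a diagnosis is itself counted as service use. Section 6.3.2 names testing and follow-up and never names diagnosis. Only item set (a) brings it in.
- A reader might infer that infections raise the measure with no gain in access. Items 5.14 and 5.16 require that a doctor or nurse told the student, so a yes implies clinical contact, and more testing also yields more diagnoses.
- A reader might infer that five of the nine items depend on harm. That holds for set (a) only.
- A reader might infer that prevention lowers the score outright. Lifetime items answered consistently cannot fall within a student. The effect is a smaller rise than under control conditions, although the intervention effect in the mixed model is that contrast.

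The registry entry for service use names neither pregnancy nor diagnosis, so its wording shares the problem only through the nine-item count.

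**Conclusion.** The point holds for pregnancy and, in a limited form, for follow-up care. Followed as written, Section 6.3.2 credits a pregnancy as service use, against the direction of the plan's own secondary outcome. Follow-up credit, if scored, depends on infection as well as access. Whether the diagnosis items are scored is not stated.

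The measure is contaminated rather than inverted, because the three testing items do record services. The 0.02 to 0.10 points for pregnancy alone rest on an assumed unweighted sum and on an assumed 2 to 10% of students averting a pregnancy. The larger figures also assume averted diagnoses and 80% follow-up. Severity is moderate: the outcome is tertiary, and the primary analysis and sample size do not depend on it.

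**What to change.** In Section 6.3.2 and Table 2:

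- Remove pregnancy (5.11) from the service-use outcome and keep it as a secondary outcome only.
- Score service use from receipt of services: 4.1, 5.12, 5.13 and 5.15. Name these items and state the scoring rule.
- Do not score 5.14 or 5.16. Report follow-up care separately, as a proportion among students who report a diagnosis.
- State how students who skip Section 5 are scored on 5.12, 5.13 and 5.15.

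Update the item count in the registry's service-use entry to match.

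The cost is wording and rescoring of items already in the survey, with no new data collection. The measure drops from nine items to four and is coarser. Follow-up care will be estimated only in the diagnosed subgroup, so with less precision.

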**Table 2. NIE Measures.**

**Table 2. N/E Measures.**

Data Collection Instruments and Measures	Data Collection: Baseline & Months				Description of Measures Number of Items; Scale Anchors; Benchmark Values	
	Base	3	9	12		
Student Survey						
Primary Outcome Variable						
Proportion of condom use during sexual intercourse (SI)	X	X	X	X	2 items; number of times condom used relative to number of times had SI	
Secondary Outcome Variables						
Age of onset of sexual intercourse	X	X	X	X	2 items; ever had SI & age at first SI	
Number of sex partners	X	X	X	X	2 items; lifetime & past-month sex partners	
Frequency of sexual intercourse	X	X	X	X	1 item; frequency of SI in past month	
Pregnancy history	X	X	X	X	1 item; number of pregnancies	
Type & frequency of birth control (BC) during sexual intercourse	X	X	X	X	3 items; type of BC use and number of times BC used during SI	
Type & frequency of substance use (SU) during sexual intercourse	X	X	X	X	1 item measures SU with SI; 5 items measure lifetime and past month SU	
Tertiary Outcome Variables						
Type & frequency of parent/legal guardian-child SRH communication	X	X	X	X	24 items Likert scale; higher score = higher communication	
Cultural identity & participation in cultural activities	X	X	X	X	3 items cultural identity ( $\alpha = .75$ ); 2 items cultural activities engagement ( $\alpha = .46$ )	
Type & frequency of SRH services	X	X	X	X	9 items; frequency, type, and follow-up of SRH services used	
Other Variables						
Motivation to avoid STIs, HIV, HCV, & pregnancy	X	X	X	X	Up to 9 items; 1 (very true) to 5 (very untrue); 1 = more positive attitude/motivation	
Condom & birth control use intention & self-efficacy	X	X	X	X	4 items per intention; 1 (very true) to 5 (very untrue); 1 = higher intention; 6 self-efficacy items; 1 (very easy) to 4 (very hard); 1 = high self-efficacy	
Abstinence	X	X	X	X	3 items; 1 (strongly disagree) to 4 (strongly agree); 4 = more supportive of teen abstinence	
Refusal skills regarding sex	X	X	X	X	7 items; 1 (I definitely can say no) to 5 (I definitely can't); 1 = stronger refusal skills	
Knowledge of STIs, HIV, HCV, pregnancy, & health relationships	X	X	X	X	Range of 4 to 10 items per topic; True/False/DK; Average proportion of questions correct	
Depression (CES-D) & exposure to stressful life events	X	X	X	X	CES-D — 7 items ( $\alpha = .80$ ); Life Events — 24 items; Yes/No; number of events observed	
Student Demographics						
Age, gender, sexual orientation, school, highest grade completed	X	X	X	X	4 items	
Parent/Legal Guardian Survey						
Type & frequency of parent/legal guardian-child SRH communication	X		X	X	24 items Likert scale; higher score = higher communication	
Parent/Legal Guardian Demographics						
Age, gender, marital status, highest grade completed, occupation	X		X	X	5 items	
Barriers/Facilitators Discussion Guide						
8 Service Domains for Evidence-Based Clinical Best Practices	X			X	Open-ended questions about barriers/facilitators for: contraceptive access, provision of hormonal contraception/IUD, emergency contraception, cervical cancer screening, STI/HIV/HCV testing and treatment, cost confidentiality, consent, health center infrastructure, & health center environment.	
Coordination & Implementation Monitoring Plan Tracking Log						
Base	3	6	9	12		
8 Service Domain Elements	X	X	X	X	Tracks action steps, timeline, and responsible party	

## 6.4 Potential Risks

There may be minor risks to agreeing to participate in N/E. Student and parent/legal guardian participants may be asked some questions that make them feel uncomfortable, sad, or confused (e.g., questions about sexual risk behaviors). For participants in the systems-level component of the study that evaluates the enhancement of the coordination of SRH services, we anticipate low to no risks, since none of the data being collected will be of a personal nature. For Aim 3, which uses focus groups as one method of data collection to evaluate the fidelity and acceptability of N/E, we also anticipate low to no risk, since none of the data being collected will be of a personal nature. All study participants will be informed that they may choose to stop their participation in N/E at any time or decline to answer a particular question asked of them on a data collection instrument or during a data collection process. We will inform study participants that the study is voluntary and that they can withdraw from the study, by stating that they want to do so, at any time over the course of the study.

### 6.4.1. Adequacy of Protection Against Risks

*Nenunkumbi/Edahiyedo ("We Are Here Now": A Mult-level, Multi-component Sexual and Reproductive Health Intervention for American Indian Youth*

## A. Recruitment and Informed Consent

The high schools in Frazer, Wolf Point, Poplar, Brockton, and Culbertson will serve as the primary recruitment sites for our study. Based on discussions with school personnel and our previously successful recruitment strategies, recruitment will occur via flyers posted in the schools, letters to the parents, parent-teacher meetings, and word of mouth. Additionally, a parent/legal guardian session that provides an overview of N/E, the content and format of the intervention components, and risk and benefits of participation will be held at each of the study's 5 schools. Students and their parents/legal guardians from each cluster will be recruited for participation at baseline (Q2 of Year 2). At the time of the student data collection at baseline, [name] and the study's outreach coordinator will thoroughly review the assent form with the students, which will include a description of the N/E curricular components, types of questions that will be asked in the data collection, and potential risks and benefits of participating in N/E. All attempts will be made to help the students understand the nature of the study. [name] and the study's outreach coordinator will thoroughly review the consent forms with the parents, which will include a description of N/E, types of questions that will be asked, and potential risks and benefits of participating in N/E. Parents will provide informed consent for their child as well as for themselves prior to their participation in the Native Voices curriculum. For the systems-level component, Epi Team members will complete an informed consent at the time of the first barriers and facilitators discussions in Year 2. If members change from one such discussion to the next, new informed consents will be collected as needed. For the Aim 3 focus groups, informed consent will be obtained from the mentors or the professionals representing agencies prior to their participation in the focus groups as key stakeholders. Consent and assent will be obtained from parents/legal guardians for their participation in a parent group, and from parents/legal guardians and their children, respectively, for the children's participation in a children's focus group. All study participants, both adults and children, will be reminded that they can withdraw at any time without consequences. No study participant will be coerced to participate in the study, in whole or in part. Human subjects approval has been received from the Fort Peck IRB for the Year/Aim 1 refining, tailoring, and finalizing the intervention design. At that point, new applications to the Fort Peck IRB and the MSU IRB will receive approvals prior to study start.
